10.2 Statistical Hypotheses

The following statistical hypotheses will be tested:

Safety Population at 6 weeks:

H_{01} : There is no difference in the proportion of subjects that experience at least one TE-SAE of a visual acuity decrease (defined as an increase of 0.22 or greater in logMAR score) categorized as probably or definitely related to IP in the 0.25% Reproxalap group vs. Vehicle group in the Safety population within 6 weeks of study drug treatment.

H_{A1} : The proportion of subjects that experience at least one TE-SAE of a visual acuity decrease (defined as an increase of 0.22 or greater in logMAR score) categorized as probably or definitely related to IP is greater in the 0.25% Reproxalap group than the Vehicle group in the Safety population within 6 weeks of study drug treatment.

H_{02} : There is no difference in the proportion of subjects that experience at least one TE-SAE of an IOP increase from baseline of ≥ 10 mm Hg AND report an IOP of > 25 mm Hg categorized as probably or definitely related to IP in the

0.25% Reproxalap group vs. Vehicle group in the Safety population within 6 weeks of study drug treatment.

H_{A2} : The proportion of subjects that experience at least one TE-SAE of an IOP increase from baseline of ≥ 10 mm Hg AND report an IOP of > 25 mm Hg categorized as probably or definitely related to IP is greater in the 0.25% Reproxalap group than the Vehicle group in the Safety population within 6 weeks of study drug treatment.

H_{03} : There is no difference in the proportion of subjects that experience at least one TE-SAE of the cornea detected via slit-lamp biomicroscopy categorized as probably or definitely related to IP in the 0.25% Reproxalap group vs. Vehicle group in the Safety population within 6 weeks of study drug treatment.

H_{A3} : The proportion of subjects that experience at least one TE-SAE of the cornea detected via slit-lamp biomicroscopy categorized as probably or definitely related to IP is greater in the 0.25% Reproxalap group than the Vehicle group in the Safety population within 6 weeks of study drug treatment.

H_{04} : There is no difference in the proportion of subjects that experience at least one TE-SAE of the retina detected via fundoscopy categorized as probably or definitely related to IP in the 0.25% Reproxalap group vs. Vehicle group in the Safety population within 6 weeks of study drug treatment.

H_{A4} : The proportion of subjects that experience at least one TE-SAE of the retina detected via fundoscopy categorized as probably or definitely related to IP is greater in the 0.25% Reproxalap group than the Vehicle group in the Safety population within 6 weeks of study drug treatment.

Long-Term Follow-up Subjects at (6 Months or 1 Year)

H_{05} : There is no difference in the proportion of subjects that experience at least one TE-SAE of a visual acuity decrease (defined as an increase of 0.22 or greater in logMAR score) categorized as probably or definitely related to IP in the 0.25% Reproxalap group vs. Vehicle group in the Safety-LTFU population within 6 months of study drug treatment (or 1 year).

H_{A5} : The proportion of subjects that experience at least one TE-SAE of a visual acuity decrease (defined as an increase of 0.22 or greater in logMAR score) categorized as probably or definitely related to IP is greater in the

0.25% Reproxalap group than the Vehicle group in the Safety-LTFU population within 6 months of study drug treatment (or 1 year).

H_{06} : There is no difference in the proportion of subjects that experience at least one TE-SAE of an IOP increase from baseline of ≥ 10 mm Hg AND report an IOP of > 25 mm Hg categorized as probably or definitely related to IP in the 0.25% Reproxalap group vs. Vehicle group in the Safety-LTFU population within 6 months of study drug treatment (or 1 year).

H_{A6} : The proportion of subjects that experience at least one TE-SAE of an IOP increase from baseline of ≥ 10 mm Hg AND report an IOP of > 25 mm Hg categorized as probably or definitely related to IP is greater in the 0.25% Reproxalap group than the Vehicle group in the Safety-LTFU population within 6 months of study drug treatment (or 1 year).

H_{07} : There is no difference in the proportion of subjects that experience at least one TE-SAE of the cornea detected via slit-lamp biomicroscopy categorized as probably or definitely related to IP in the 0.25% Reproxalap group vs. Vehicle group in the Safety-LTFU population within 6 months of study drug treatment (or 1 year).

H_{A7} : The proportion of subjects that experience at least one TE-SAE of the cornea detected via slit-lamp biomicroscopy categorized as probably or definitely related to IP is greater in the 0.25% Reproxalap group than the Vehicle group in Safety-LTFU population within 6 months of study drug treatment (or 1 year).

H_{08} : There is no difference in the proportion of subjects at least one TE-SAE of the retina detected via fundoscopy categorized as probably or definitely related to IP in the 0.25% Reproxalap group vs. Vehicle group in the Safety-LTFU population within 6 months of study drug treatment (or 1 year).

H_{A8} : The proportion of subjects at least one TE-SAE of the retina detected via fundoscopy categorized as probably or definitely related to IP is greater in the 0.25% Reproxalap group than the Vehicle group in the Safety-LTFU population within 6 months of study drug treatment (or 1 year).

10.3 Sample Size

6 Week:

[figure not shown]
[figure not shown]
[figure not shown]
[figure not shown]
[figure not shown]

Table 1: Assumed True Event Proportions

[figure not shown]
[figure not shown]
[figure not shown]

6 Months (26 weeks) and 1 Year:

Table 2: Assumed True Event Proportions

10.4 Statistical Analysis

10.4.1 General Considerations

Quantitative variables will be summarized using number of subjects (n), mean, median, standard deviation, minimum and maximum. The dichotomous variables will be summarized using counts and percentages.

Summaries will be provided for demographics, baseline medical history, concurrent therapies, and subject disposition.

Baseline measures are defined as the last measure prior to the administration of study treatment at Visit 1 (Day 1). Change from baseline will be calculated as Visit – Baseline.

For the purpose of summarization, medical history, concurrent therapies, and AEs will be coded to MedDRA and WHO Drug dictionaries, as appropriate.

[figure not shown]
[figure not shown]
[figure not shown]
10.4.2 Unit of Analysis

Safety endpoints will be analyzed for both eyes. For subject-level efficacy endpoints, the unit of analysis will be the subject. For endpoints assessed on each eye individually, the unit of analysis will be right eye (OD) or left eye (OS).

[figure not shown]
10.4.3 Missing Data

All primary and other safety analyses will be executed using observed data only for both Safety Population and Safety-LTFU population. Sensitivity analyses including treatment of missing data will be outlined in the SAP.

10.4.4 Multiplicity Adjustments

A large rectangular area of the page is completely blacked out, indicating that the content has been redacted.A large rectangular area of the page is completely blacked out, indicating that the content has been redacted.A large rectangular area of the page is completely blacked out, indicating that the content has been redacted.

10.4.5 Primary Safety Analyses

A large rectangular area of the page is completely blacked out, indicating that the content has been redacted.

The primary safety comparisons in this trial will be between 0.25% Reproxalap versus Vehicle in the Safety Population using the following primary estimand:

Estimand 1

- Populations:
 - Subjects with DED defined through enrollment criteria that are enrolled in either the 6-week follow-up or 1-year follow-up schedule.
 - Subjects with DED defined through enrollment criteria that are enrolled in the 1-year follow-up schedule only.
- Endpoints:

Safety population at 6 weeks:

- Proportion of subjects that experience at least one TE-SAE of a visual acuity decrease (defined as an increase of 0.22 or greater in logMAR score) categorized as probably or definitely related to IP within 6 weeks of study drug dosing in the Safety population
- Proportion of subjects that experience at least one TE-SAE of an IOP increase from baseline of ≥ 10 mm Hg AND report an IOP of > 25 mm Hg categorized as probably or definitely related to IP within 6 weeks of study drug dosing in the Safety population
- Proportion of subjects that experience at least one TE-SAE of the cornea detected via slit-lamp biomicroscopy categorized as probably or definitely related to IP within 6 weeks of study drug dosing in the Safety population
- Proportion of subjects that experience at least one TE-SAE of the retina detected via fundoscopy categorized as probably or definitely related to IP within 6 weeks of study drug dosing in the Safety population

Safety-LTFU population within 6 months (or 1 year):

- Proportion of subjects that experience at least one TE-SAE of a visual acuity decrease (defined as an increase of 0.22 or greater in logMAR score) categorized as probably or definitely related to IP within 6 months/1 year of study drug dosing in the Safety-LTFU population
- Proportion of subjects that experience at least one TE-SAE of an IOP increase from baseline of ≥ 10 mm Hg AND report an IOP of > 25 mm Hg categorized as probably or definitely related to IP within 6 months/1 year of study drug dosing in the Safety-LTFU population
- Proportion of subjects that experience at least one TE-SAE of the cornea detected via slit-lamp biomicroscopy categorized as probably or definitely related to IP within 6 months/1 year of study drug dosing in the Safety-LTFU population
- Proportion of subjects that experience at least one TE-SAE of the retina detected via fundoscopy categorized as probably or definitely related to IP

within 6 months/1 year of study drug dosing in the Safety-LTFU population

- Intercurrent event:
 - Discontinuation of study medications is ignored, measures obtained after discontinuation of study medication will be analyzed. [treatment policy strategy]
 - Non-optimal compliance is ignored, measures will be analyzed regardless of treatment compliance. [treatment policy strategy]
 - Use of prohibited alternative therapies is ignored, measures obtained after initiation of prohibited therapies will be analyzed. [treatment policy strategy]
 - Discontinuation of study, subjects that discontinue study prior to time point of interest for an endpoint (Ex. 6 weeks or 6 months/1 year) AND do not experience event of interest will not be analyzed. [principal stratum strategy]
 - Discontinuation of study, values post-discontinuation will not be imputed. [while on treatment strategy]
- Population-level summaries:
 - Difference in the proportion of subjects that experience at least one TE- SAE of a visual acuity decrease (defined as an increase of 0.22 or greater in logMAR score) categorized as probably or definitely related to IP
 - Difference in the proportion of subjects that experience at least one TE- SAE of an IOP increase from baseline of ≥ 10 mm Hg AND report an IOP of > 25 mm Hg categorized as probably or definitely related to IP
 - Difference in the proportion of subjects that experience at least one TE- SAE of the cornea detected via slit-lamp biomicroscopy categorized as probably or definitely related to IP
 - Difference in the proportion of subjects with at least one TE-SAE of the retina detected via fundoscopy categorized as probably or definitely related to IP

Sensitivity analyses of the primary safety endpoints may include repeating primary analyses with alternative handling of intercurrent events with different estimands. In addition, sensitivity analyses using incidence rates (events/person-time) will be produced. Details will be outlined in the SAP.

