5.5 Withdrawal Criteria (if applicable)

If at any time during the study the investigator determines that a subject's safety has been compromised, the subject may be withdrawn from the study.

Subjects may withdraw consent from the study at any time.

Sponsor and/or investigator may discontinue any subject for non-compliance or any valid medical reason (see Section 8.6.2).

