8.3 Examination Procedures

[figure not shown]
[figure not shown]
8.3.1 Procedures to be Performed at Each Study Visit with Regard to Study Objective(s)

The following procedures will be performed (see Appendix 2 for description):

Visit 1 (Day 1): Screening & Randomization

[figure not shown]
- Informed consent / Health Information Portability and Accountability Act (HIPAA);

[figure not shown]

- Qualified subjects will be scheduled for Visit 2.

[figure not shown]
[figure not shown]
Visit 2 (Day 29 ±3 days): 4-Week Follow-up

- Schedule subjects for Visit 3.

[figure not shown]
Visit 3 (Day 43 ± 4 days): 6-Week Follow-Up

- Schedule subjects for Visit 4.

[figure not shown]
Visit 4 (Day 90 ± 7 days): 3-Month Follow-up

Long-Term Follow-up (LTFU) Subjects Only

Visit 5 (Day 180 ± 7 days): 6-Month Follow-up

Long-Term Follow-up (LTFU) Subjects Only

[figure not shown]

Schedule subjects for Visit 6.

Visit 6 (Day 270 ± 10 days): 9-Month Follow-up

[figure not shown]
Long-Term Follow-up (LTFU) Subjects Only

[figure not shown]

- Schedule subjects for Visit 7.

Visit 7 (Day 360 ± 10 days): 1-Year Follow-up

Long-Term Follow-up (LTFU) Subjects Only

- Study Exit

Early Termination/Discontinuation

If a subject is discontinued from the study prior to Visit 7 (Day 360 ± 10), then all safety evaluations that are to be performed at Visit 7 should be performed on the day of discontinuation (early termination) or at the discretion of the investigator.

Adverse Events (both elicited and observed) and SAEs will be monitored throughout the study. The investigator will promptly review all adverse events (both elicited and observed) for accuracy and completeness. All adverse events will be documented on the appropriate source document and eCRF. If a female reports a pregnancy or has a positive pregnancy test during the study, then the investigator will notify [REDACTED] immediately. The investigator shall instruct the patient to immediately stop the study medication and request from the subject and/or the subject's physician copies of all related medical reports during the pregnancy and shall document the outcome of the pregnancy. The investigator will retain these reports together with the subject's source documents and will provide a copy of all documentation to [REDACTED]

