8.6.2 Discontinued Subjects

Subjects may be discontinued prior to their completion of the study due to:

- adverse events;
- protocol violations;
- administrative reasons (e.g., inability to continue due to scheduling changes);
- lost to follow up;
- sponsor termination of study;
- subject choice (e.g. withdrawal of consent); and
- other

Note: In addition, any subject may be discontinued for any sound medical reason at the discretion of the investigator.

Discontinuations that are the direct result of SARS-CoV-2 (COVID-19) will be classified separately and clearly documented in the eCRF. A separate field will be completed to denote a COVID-19 related discontinuation and the specific reason will be documented utilizing the above noted list of subcategories.

Notification of a subject discontinuation and the reason for discontinuation will be made to [REDACTED] study sponsor and will be clearly documented on the eCRF.

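### The treatment-policy estimand is not secured: subjects may be taken out of the study for events it says are ignored, and event-free leavers are then excluded

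*Combined protocol and SAP*

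**What the plan says.** Section 10.4.5 (repeated in the Synopsis) lists the intercurrent events for Estimand 1. Three carry a treatment-policy label:

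- Stopping study drug: "Discontinuation of study medications is ignored, measures obtained after discontinuation of study medication will be analyzed".
- Poor compliance: "Non-optimal compliance is ignored, measures will be analyzed regardless of treatment compliance".
- Prohibited therapy: handled in the same way, with later measures used.

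Leaving the study is a separate event. Subjects who leave before the time point of interest "AND do not experience event of interest will not be analyzed". Section 10.4.3 adds: "All primary and other safety analyses will be executed using observed data only".

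The conduct sections describe who may leave and what happens next:

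- Section 5.5: "Sponsor and/or investigator may discontinue any subject for non-compliance or any valid medical reason", with a pointer to Section 8.6.2.
- Section 8.6.2: "Subjects may be discontinued prior to their completion of the study due to" a list of reasons that includes adverse events and protocol violations.
- Section 8.6.1 defines a completer by study status alone.
- Section 8.3.1, for a subject who leaves before Visit 7: "all safety evaluations that are to be performed at Visit 7 should be performed on the day of discontinuation", or at the investigator's discretion.
- Section 4 asks early terminators for safety assessments before they begin another dry-eye therapy, if possible.

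**The concern.** A treatment-policy strategy needs subjects to be examined after the intercurrent event. The four primary endpoints depend on visual acuity, IOP, slit-lamp and fundoscopy findings, so the subject has to attend. The visible conduct text asks for no visit after exit, and it permits exit for reasons that overlap with the events the estimand says are ignored.

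A subject taken out for such an event, and event-free at that point, moves from a rule that keeps them to a rule that drops them. Two sites could follow the protocol correctly and handle the same subject differently. In a trial whose only objective is comparative safety, the primary proportions would then depend partly on discretionary removals. No later analysis can recover examinations that were not done.

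**Working it through.** There is no plan figure to reproduce. The point rests on wording, and the assumed event proportions and sample-size text are not shown in the public copy.

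**Step 1: the rules side by side.**

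| Event | Estimand 1 | Conduct text | Result if removed from the study while event-free |
|---|---|---|---|
| Non-compliance | Ignored | 8.5: deviation recorded; 5.5: may be discontinued | Not analysed at later time points |
| Drug stopped (e.g. after an adverse event) | Ignored | 8.6.2: adverse events may lead to study discontinuation | Not analysed at later time points |
| Prohibited therapy | Ignored | 8.6.2: protocol violations may lead to study discontinuation; 4: exit assessment before the other therapy starts | Not analysed at later time points |

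The match is explicit for non-compliance. For the other two it is indirect, through adverse events, protocol violations or a medical reason.

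**Step 2: trace one subject.** A long-term subject stops drops in month 3 and has had no qualifying event. If kept in the study, the subject counts in the 6-month and 1-year proportions. If discontinued from the study, the subject has one exit assessment and is absent from both. The 6-week proportion is unaffected here; it is exposed only to exits before week 6.

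**Step 3: scale.** Section 5.1 gives about 550 long-term subjects at 2:1, so 550 × 2/3 ≈ 367 on reproxalap, with a goal of at least 100 completers. The goal could be met with 267/367 ≈ 73% not completing. That is arithmetic on a floor, not a forecast, and it does not say why subjects would leave.

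**Step 4: bias if exit is unrelated to risk (assumed values).** Let r be the true risk over the period and d the exit probability, with constant, independent hazards:

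- λ = −ln(1 − r), μ = −ln(1 − d)
- E (event before exit) = λ/(λ + μ) × [1 − exp(−(λ + μ))]
- C (completes event-free) = exp(−(λ + μ)) = (1 − r)(1 − d)
- Analysed proportion = E/(E + C)

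For r = 1% and d = 20%: λ = 0.01005, μ = 0.22314, C = 0.99 × 0.80 = 0.792, and E = (0.01005/0.23319) × 0.208 = 0.00896. The analysed proportion is 0.00896/0.80096 = 1.12%.

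| Exit d | 5% | 10% | 20% | 30% | 50% |
|---|---|---|---|---|---|
| Analysed, true 1% | 1.03% | 1.05% | 1.12% | 1.20% | 1.44% |

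The rule keeps events that precede exit but drops event-free leavers, so the proportion rises. With equal true risk in both arms and exit of 20% against 5%, the arms differ falsely by 1.12% − 1.03% = 0.09 points at 1% risk, and by 5.57% − 5.12% = 0.45 points at 5% risk.

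**Step 5: bias if leavers carry more risk (assumed values).** Suppose a share d leaves before any event with k times the risk s of those who stay. Then r = d·k·s + (1 − d)·s, so s = r/(1 − d + d·k), and s is what is analysed. For r = 1% and d = 20%:

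- k = 2: 0.01/(0.80 + 0.40) = 0.83%
- k = 4: 0.01/(0.80 + 0.80) = 0.63%

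Here the risk is understated.

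**The case against.** The opposing case is substantial.

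- **Removal is discretionary.** Sections 5.5 and 8.6.2 say that subjects may be discontinued, and Section 8.5 attaches only a recorded deviation to non-compliance. The pregnancy instruction in Section 8.3.1 stops the drug without stating study exit. A reader might infer that off-drug data will largely not exist. The text does not support that: no rule equates stopping drug with leaving the study.
- **Analysis already separates the two.** Estimand 1 lists them as different events, and Section 10.4.6 tabulates treatment discontinuation and its primary reason. The case report form may already capture both.
- **Exclusion is limited.** A reader might infer that everyone who leaves is deleted. Only event-free early leavers are dropped, and only from the primary proportions. Subjects with a prior event stay in, adverse-event tables are produced separately, and person-time rates are planned as a sensitivity analysis.
- **Redaction.** Visit procedures, and text following the early-termination sentence in Section 4, are blacked out. A retention instruction could be there.
- **Size.** A reader might apply an assumed drug-stop rate to the 367 and call the result lost subjects. That presumes every subject who stops drops also leaves the study, which is the open question.

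All of this limits the claim, but it does not remove the gap. Person-time rates use time up to exit and cannot supply later events. The telephone follow-up in Section 9.5 covers only subjects with an adverse event and cannot measure IOP or examine a retina. Tabulating drug discontinuation does not create visits.

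**Conclusion.** The concern holds in a limited form: continued follow-up after an ignored event is not secured by the visible text, and the outcome for an event-free subject turns on whether the site or sponsor uses its discretion to end participation. The documents do not show that such removals will be common, so the number affected is unknown.

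The direction of bias is also unknown. At a true risk of 1% and 20% exit, the illustrations run from 0.63% to 1.12%. They rest on assumed risks, assumed exit rates, and either independent exit or leavers at 2 to 4 times the risk of those who stay. A reader might infer that harm is necessarily understated; that follows only if leavers carry higher risk, and the documents give no evidence on this. The conclusion would fall away if a redacted section already keeps these subjects on schedule.

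**What to change.** Reconcile Sections 4, 5.5, 8.3.1, 8.6.2 and 10.4.5:

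1. State in Sections 5.5, 8.3.1 and 8.6.2 that stopping study drug, non-compliance or use of a prohibited therapy is not in itself a reason to leave the study, and that such subjects are asked to attend the remaining scheduled safety visits.
2. Record drug stop and study exit as separate events, each with its own date and reason, in the conduct sections, as the analysis section already assumes.
3. If a redacted section already says this, cross-refer to it from the estimand.

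Who stops treatment, and removal for medical or safety reasons, stay with the investigator and sponsor. The cost is a short amendment, possibly a case report form field, and some already scheduled visits attended off drug.

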Other safety endpoints will be summarized by treatment group and visit using descriptive statistics using the Safety population or Safety-I.TFU population. Changes or shifts from baseline will also be summarized where appropriate. Assessments performed by eye will be summarized separately for right eye (OD) and left eye (OS).

For quantitative safety endpoints, comparisons between treatment groups will be made at the eye level. [REDACTED]

[REDACTED]

Summary of Known and Potential Risks and Benefits to Human Subjects

There are no known safety risks of topical ocular reproxalap, which has been administered to 968 subjects across 8 Phase 2 and Phase 3 clinical trials in concentrations of 0.1%, 0.25%, and 0.5%, up to 4-times-daily for 12 weeks and 8-times-daily tapered to 4-times-daily over 4 weeks in healthy volunteers and in subjects with dry eye disease, allergic conjunctivitis, and noninfectious anterior uveitis. No consistent changes in visual acuity, slit-lamp evaluation, IOP, dilated fundoscopy, or non-ocular adverse events have been observed. No treatment-related serious adverse events have been observed. [REDACTED]

[REDACTED]

Reproxalap has demonstrated consistent, statistically significant, and clinically meaningful activity in dry eye disease, allergic conjunctivitis, and noninfectious anterior uveitis as assessed by change from baseline and improvement over vehicle.

TABLE OF CONTENTS

SYNOPSIS	4
TABLE OF CONTENTS	16
LIST OF ABBREVIATIONS	20
1 INTRODUCTION	21
2 STUDY OBJECTIVES	22
3 CLINICAL HYPOTHESES	22
4 OVERALL STUDY DESIGN	22
5 STUDY POPULATION	24
5.1 Number of Subjects (approximate)	24
5.2 Study Population Characteristics	24
5.3 Inclusion Criteria	25
5.4 Exclusion Criteria	25
5.5 Withdrawal Criteria (if applicable)	26
6 STUDY PARAMETERS	27
6.1 Efficacy Measures	27
6.2 Safety Measures	27
6.3 Other Measures	27
7 STUDY MATERIALS	28
7.1 Study Drug(s)	28
7.1.1 Study Drug(s)/ Formulation(s)	28
7.1.2 Study Drug Packaging Configuration	28
7.1.3 Study Drug Storage and Accountability	28
7.1.4 Instructions for Dispensation, Use, and Administration	28
7.2 Other Study Supplies	29
8 STUDY METHODS AND PROCEDURES	29
8.1 Subject Entry Procedures	29
8.1.1 Overview	29
8.1.2 Informed Consent	29
8.1.3 Washout Intervals	29
8.1.4 Procedures for Final Study Entry	29
8.1.5 Methods for Assignment to Treatment Groups:	29
8.2 Concurrent Therapies	30

8.2.1	Prohibited Medications/Treatments	30
8.2.2	Escape Medications	30
8.2.3	Special Diet or Activities	30

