5 STUDY POPULATION

5.1 Number of Subjects (approximate)

It is estimated that approximately 1050 subjects will be screened to enroll approximately 850 subjects in a 2:1 ratio of reproxalap to vehicle. Approximately 550 subjects will continue after Week 6 for long-term follow-up, with the goal of at least 100 reproxalap subjects completing the long-term follow-up.

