9 ADVERSE EVENTS

9.1 Adverse Event

An adverse event is defined as any untoward medical occurrence associated with the use of a drug in humans, whether or not the event is considered IP-related. An adverse event can therefore be any unfavorable and unintended sign (e.g., an abnormal laboratory finding), symptom, or disease occurring after the subject started dosing with the IP,

without any judgment about causality. An AE can arise from any use of the IP (e.g., off-label use, use in combination with another drug or medical device) and from any route of administration, formulation, or dose, including an overdose. An AE can arise from any delivery, implantation, or use of a medical device, including medical device failure, subject characteristics that may impact medical device performance (e.g., anatomical limitations), and therapeutic parameters (e.g., energy applied, sizing, dose release, and anatomic fit) associated with medical device use.

All AEs spontaneously reported by the subject and/or in response to an open question from study personnel or revealed by observation, physical examination or other diagnostic procedures will be recorded in the source document and on the appropriate pages of the CRF. Any clinically relevant deterioration in clinical finding is considered an AE and must be recorded. When possible, signs and symptoms indicating a common underlying pathology should be noted as one comprehensive event.

Any pre-existing medical condition that worsens after administration of the IP will also be considered a new adverse event.

[figure not shown]
If there is a worsening of a medical condition that was present prior to the administration of the IP, this should also be considered a new adverse event and reported. Any medical condition present prior to the administration of the IP that remains unchanged or improved should not be recorded as a treatment emergent adverse event at subsequent visits unless it worsens during treatment.

[figure not shown]
Investigational Product (IP) includes the investigational drug under evaluation and placebo, or any other medications required by the protocol given during any stage of the study.

Documentation regarding the adverse event should be made as to the nature, date of onset, end date, severity, relationship to IP, action(s) taken, seriousness, and outcome of any sign or symptom observed by the physician or reported by the patient upon indirect questioning.

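### Estimand 1 drops study leavers without the event but keeps those with it, so the tested proportions depend on dropout, and study discontinuation carries two strategy labels

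*Combined protocol and SAP*

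**What the plan says.** Section 10.4.5 defines Estimand 1, and the synopsis repeats it. Three of its intercurrent-event bullets matter here.

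- Stopping study medication: "measures obtained after discontinuation of study medication will be analyzed. [treatment policy strategy"].
- Leaving the study before 6 weeks, or before 6 months or 1 year: such subjects who also "AND do not experience event of interest will not be analyzed. [principal stratum strategy"].
- Leaving the study, again: "Discontinuation of study, values post-discontinuation will not be imputed. [while on treatment strategy"].

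The same section adds that "sensitivity analyses using incidence rates (events/person-time) will be produced", and that other estimands may be explored. Section 10.1 defines the Safety and Safety-LTFU populations by treatment and one post-dose safety measurement, with no requirement to complete. Section 10.4.3 limits the analyses to observed data and leaves missing-data sensitivity analyses to the SAP. The synopsis gives the SAP precedence over the protocol's statistical text.

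**The concern.** Both conditions must hold for a subject to be removed: leaving early and having no event. A subject who has the event in month 2 and leaves in month 3 counts. A subject who leaves in month 3 without it disappears, together with the event-free time already observed. Whether a subject is analysed thus depends on the outcome being measured.

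The principal-stratum label does not describe this. A principal stratum is defined by what discontinuation would have been under both treatments. The rule instead uses observed dropout and observed outcome in the assigned arm. The second label, while on treatment, is attached to the same intercurrent event, and it sits badly beside the treatment-policy handling of stopped medication. The rule also does not match the all-treated populations in Section 10.1.

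In a safety comparison the consequences run both ways. If the arms lose different numbers of subjects, the difference is biased, and harm can be partly hidden if vehicle loses more. If they lose equal numbers, a real absolute difference is magnified.

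**Working it through.** **Inputs.** Section 5.1 says: "Approximately 550 subjects will continue after Week 6 for long-term follow-up". At 2:1, with randomization stratified by follow-up schedule (Section 8.1.5), this is 550 × 2/3 ≈ 367 reproxalap and 550/3 ≈ 183 vehicle. Retention and event risks are not readable, and the plan states no figure to reproduce for this rule, so both are assumed and varied.

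**Model.** Constant, independent hazards over the period, with h = −ln(1 − risk) and d = −ln(retention).

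- Observed events: o = h/(h+d) × (1 − e^−(h+d))
- Event-free completers: c = e^−(h+d)
- Proportion under the rule: o/(o+c)

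Example with 2% risk and 70% retention: h = 0.0202 and d = 0.3567. Then c = 0.98 × 0.70 = 0.686 and o = (0.0202/0.3769) × 0.314 = 0.0168. The rule gives 0.0168/0.7028 = 2.39%.

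**One arm**

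| True risk | 95% retained | 90% | 80% | 70% | 50% |
|---|---|---|---|---|---|
| 2% | 2.05% | 2.11% | 2.24% | 2.39% | 2.86% |
| 1% | 1.03% | 1.05% | 1.12% | 1.20% | 1.44% |

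A simpler model agrees. Let half of the leavers' events fall before exit and let x be the dropout share. The proportion is then [p(1−x) + 0.5px]/[(1−x) + 0.5px]. With p = 2% and x = 30%, this is 0.017/0.703 = 2.42%.

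**Two arms (reproxalap/vehicle)**

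| True risks | Retention | Reads | Difference (points) |
|---|---|---|---|
| 2% / 2% | 95% / 90% | 2.05% / 2.11% | −0.06 (true 0) |
| 2% / 2% | 70% / 50% | 2.39% / 2.86% | −0.47 (true 0) |
| 3% / 1.5% | 80% / 60% | 3.35% / 1.95% | 1.40 (true 1.5); RR 1.7 (true 2.0) |
| 3% / 1.5% | 80% / 40% | 3.35% / 2.44% | 0.92 (true 1.5); RR 1.4 (true 2.0) |
| 3% / 1.5% | 70% / 70% | 3.59% / 1.80% | 1.79 (true 1.5); RR 2.0 (true 2.0) |

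For the equal-risk rows, swapping the retentions reverses the sign. In subjects, the 80%/40% row is 9.9 events and 284.8 completers of 367 (72 excluded), against 1.8 events and 72.1 completers of 183 (109 excluded).

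**Does follow-up time cure it?** In simulations of 2,000,000 subjects per case, 1 − exp(−events/person-time) returned 2.02% for a true 2% at 50% retention (rule 2.88%). It returned 1.51% for a true 1.5% at 40% retention (rule 2.45%).

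**When the rule does not inflate.** There is no inflation with zero events, no dropout, or dropout at the very start. Nor is there any if leavers' later hazard is high enough. The break-even multiple of the on-study hazard, at 2% on-study risk, is 2.07, 2.16, 2.27 and 2.58 at 90%, 80%, 70% and 50% retention.

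**Zero events, 367 subjects, exact upper 97.5% bound.**

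- Completers only: 1 − 0.025^(1/(367 × retention)) gives 1.4% at 70% retention and 2.0% at 50%.
- All person-time: 1 − exp(−3.689/(367 × (1 − retention)/d)) gives 1.2% and 1.4%.

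**The case against.** **The test would rarely change.** With true risks of 3.0% and 1.5% in 367 and 183 subjects, and assuming Fisher's exact test at 0.0335/4, the chance of rejection is only about 2.5% with almost no dropout. Under the rule it is about 0.4% at 80%/60% retention and under 0.1% at 80%/40%. At risks of 1% or less, false rejection also stays near zero. This stands: for rare events the damage is to the estimates, mostly tenths of a point. It is not universal. With 5% risk in both arms and 60% versus 30% dropout, simulated false rejection toward reproxalap harm was about 2.3%, against a nominal 0.42% (0.0335/8).

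**The larger figures come from chosen inputs.** Nothing in the document suggests a 40-point retention gap, and at 95%/90% the distortion is 0.06 points. The endpoints are narrow, and the synopsis says of earlier trials: "No treatment-related serious adverse events have been observed". Zero events is therefore realistic, although serious is not the same as severe and exposure there was shorter. The 80%/40% row should be read as a stress case. Against this, Section 5.1 sets a goal of at least 100 reproxalap subjects completing, about 27% of 367. That is a floor and not a forecast, but it does not promise high one-year retention.

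**Other analyses are planned.** Person-time rates, possible alternative estimands, unspecified missing-data analyses in the SAP, and the adverse-event tables in Section 10.4.6 would help expose a distortion. None replaces the primary tested result. The public document shows no separate SAP text on the rule, so a later correction cannot be excluded.

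**The bullets can be programmed together.** One says who is removed and the other says nothing is imputed for those kept. Stopping medication and leaving the study are also different intercurrent events, so they may carry different strategies. Both points are fair. The wrong principal-stratum label and the double label for one event remain.

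**Detection is by examination.** Section 8.3.1 asks for the Visit 7 safety evaluations at early exit, so events may be found at exit and hazards need not be constant. This limits how literally the figures can be taken. It does not make the inclusion rule sound.

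**Conclusion.** The concern holds and should be fixed. It is certain from the text that inclusion depends on the outcome and that study discontinuation carries two strategy labels. The size is less certain.

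If dropout is spread over follow-up and not strongly informative, event proportions are overstated by about 5% in relative terms at 90% retention (2.11/2.00), 20% at 70% (2.39/2.00) and 43% at 50% (2.86/2.00). Bias in the arm difference depends on unequal retention and can go either way. The 6-week analysis is probably little affected, so the weight falls on 6 months and 1 year. If no events occur, the cost is a wider upper bound only.

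**What to change.** Remove the exclusion of event-free leavers and the principal-stratum label, and give study discontinuation one strategy, in both the synopsis and Section 10.4.5. Confirm whether the SAP repeats the rule and, if so, change it there too, since the SAP takes precedence.

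Keep every treated subject in the Safety and Safety-LTFU populations and censor event-free leavers at their last assessment. Estimate the cumulative incidence of first event at 6 weeks, 6 months and 1 year by Kaplan-Meier, or Aalen-Johansen if deaths occur. Report the arm difference with a confidence interval, and use an exact person-time interval if an arm has no events. Promoting the planned person-time analysis to primary is an acceptable alternative. The present rule can remain as a labelled sensitivity analysis.

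Add a sensitivity analysis for informative dropout, for example with a post-dropout hazard of 1, 2 and 3 times the on-study hazard, varied by arm. It is needed because adverse events head the reasons in Section 8.6.2 ("Subjects may be discontinued prior to their completion of the study due to"), and because the proposed primary analysis assumes non-informative censoring. At 50% retention with leavers at 2.58 times the hazard, Kaplan-Meier targets 2.00% when the truth is 2.86%.

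The cost is protocol and SAP wording, one standard time-to-first-event program and one extra analysis. No new data are needed, since Section 9.1 already requires "nature, date of onset, end date, severity, relationship to IP" for each adverse event.
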